4.2 EXCLUSION CRITERIA

1. Presence of visceral lesions (e.g. lung, liver) detectable on baseline imaging or bone lesions requiring focal radiation treatment at the time of study entry
2. History of seizure or condition that may pre-dispose to seizure (e.g., prior stroke within 1 year prior to randomization, brain arteriovenous malformation, Schwannoma, meningioma, or other benign CNS or meningeal disease which may require treatment with surgery or radiation therapy).
3. Concurrent therapy with any of the following (all must have been discontinued or substituted for at least 1 week prior to randomization, except for medications known to lower seizure threshold which must be discontinued or substituted at least 4 weeks prior to randomization):
 - a. Medications known to lower the seizure threshold (for a complete list please see [Appendix 5](#))

- b. Herbal (e.g., saw palmetto) and non-herbal (e.g., pomegranate) products that may decrease PSA levels.
 - c. Systemic (oral/IV/IM) corticosteroids. Patients on chronic stable dose of steroids at an equivalent dose of prednisone \leq 10 mg daily may be permitted to enroll at the discretion of Principal Investigator.
 - d. Any other experimental treatment on another clinical trial.
- 4. Any of the following within 6 months prior to randomization: Severe/unstable angina, myocardial infarction, symptomatic congestive heart failure, arterial or venous thromboembolic events (e.g., pulmonary embolism, cerebrovascular accident including transient ischemic attacks), or clinically significant ventricular arrhythmias
- 5. Uncontrolled hypertension at study entry. Patients with a history of uncontrolled hypertension are allowed provided blood pressure is controlled by anti-hypertensive treatment.
- 6. Gastrointestinal disorder affecting absorption.
- 7. Secondary malignancy requiring active treatment except for non-melanoma skin cancer and superficial bladder cancer.
- 8. Any medical condition that would be a contra-indication to radiation therapy, such as inflammatory bowel disease.
- 9. Spinal cord compression or impending spinal cord compression
- 10. Any other condition that, in the opinion of the Investigator, would impair the patient's ability to comply with study procedures.

4.3 DURATION OF THERAPY

Protocol therapy will continue until the first occurrence of any one of the following:

- Disease progression by PCWG3 criteria
- Unacceptable adverse event(s) related to apalutamide or SBRT
- Completion of treatment (52 weeks)
- Patients decides to withdraw from the study
- Significant patient non-compliance with protocol
- General or specific changes in the patients' condition render the patient unacceptable for further treatment in the judgment of the investigator.

4.4 DURATION OF FOLLOW UP

For safety follow up, patients will be followed for adverse events until 30 days after completion of treatment, removal from study, or until death, whichever occurs first. Patients removed from study for unacceptable treatment related adverse event(s) will be followed until resolution or stabilization of all treatment related adverse events to Grade 2 or lower.

Patients will be followed on study until confirmed PSA progression by PCWG criteria.

4.5 RANDOMIZATION PROCEDURES

Once eligibility is confirmed, subjects will be randomized with equal probability to 1 of the 2 treatment arms. Balance in treatment assignment will be achieved using a randomized block design. Randomization will be carried out via computer generated random assignment. All subjects must commence treatment within 7 calendar days after randomization. Study sites will email the Eligibility Checklist to the Lead site (UCSF) in order to obtain the subject's treatment assignment. Once subject eligibility is confirmed by the lead site, an email with the treatment assignment number will be provided to the study site.

4.6 STUDY TIMELINE

The estimated study duration is approximately 36 months, 18 months for accrual and 18 months of study follow up.

5 STUDY TREATMENTS

5.1 RANDOMIZATION

After patients have provided their written informed consent, completed all screening assessments and received confirmation of eligibility, they will be randomized into the study. All patients must commence treatment within 7 calendar days after randomization.

5.2 BLINDING

There is no blinding for this study.

5.3 FORMULATION

5.3.1 Apalutamide

Refer to the Investigator's Brochure for a list of excipients.

5.3.2 Packaging, Storage, and Labeling

The apalutamide 60-mg tablets will be packaged in 120-count, 160 cc high-density polyethylene (HDPE) bottles with child-resistant caps. Bottles will include desiccant.

Each bottle of study drug will be labeled with the required regulatory agency warning statement, the protocol number, the Sponsor's name, and directions for patient use and storage. The Investigator will ensure that the study drug is stored in appropriate conditions in a secure location with controlled access. For clinical formulation-specific and batch-specific storage instructions, see the packaging label.

5.3.3 Drug Administration

Apalutamide tablets will be administered orally on a continuous daily dosing regimen at a dose of 240 mg per day (4 x 60-mg tablets) with or without food.

5.3.4 Cycle Management

For the purposes of the study, a treatment cycle will consist of 4 weeks (28 days).

It is anticipated that individual patients may occasionally forget to take a dose. In those cases, missed doses should only be replaced if the patient remembers within a 12-hour window. After that, patients should just take the next dose the following day, without compensating for the missed dose (including vomited doses). In the event of dose delays due to transient toxicity, tumor assessments should remain on schedule independent of cycle length.

5.3.5 Dose Modifications

Intra-patient dose interruptions and/or reductions will be permitted provided that study discontinuation criteria have not been met (please see Section 10).

- Patients experiencing treatment-related seizure of any grade will have study drug permanently discontinued.
- For patients experiencing Grades 1-2 treatment-related adverse events, short treatment breaks can be instituted as per the discretion of the Investigator until the severity of the toxicity decreases to Grade 1 or returns to baseline. If toxicity recurs, dose reductions to the next lower dose level will be allowed as per the discretion of the Investigator.
- For patients experiencing Grade 3 treatment-related adverse events other than seizure, study drug should be held. If the severity of the toxicity decreases to Grade 1 or returns to baseline within two weeks, study treatment may be resumed at the next lower dose level, except for clinically insignificant laboratory abnormalities that resolve within two days on optimal treatment, in which case dose reduction is not required. If toxicity recurs at Grade 3 or higher, the dose of apalutamide should be reduced to the next lower dose level. A maximum of 2 dose level reductions will be allowed (Table 1).
- For patients experiencing Grade 4 treatment-related adverse events, except for clinically insignificant laboratory abnormalities that resolve within two days on optimal treatment, study treatment must be permanently discontinued.
- Any patient requiring > 14 days delay in treatment due to study treatment-related AEs should discontinue treatment of the study treatment thought to be responsible for the AE.

Table 1 Apalutamide Dose Levels

Dose Level	Total Daily Dose	Number of 60-mg Tablets (QD)
0	240 mg	4
-1	180 mg	3
-2	120 mg	2

Doses reduced for study treatment-related toxicities should generally not be re-escalated, however, re-escalation back to the previous dose level may be permitted at the discretion of the Principal Investigator.

Rash

Dose modifications for rash are allowed only for apalutamide and are summarized in below table. If the skin rash has any component of desquamation, mucosal involvement, or pustules, stop dosing with apalutamide, refer to dermatologist for evaluation, and a skin biopsy is recommended (in addition to the interventions listed in below Table). If the skin rash is Grade 3 or higher, asking the subject to consent to documentation by a photograph and further evaluation by a dermatologist should also be considered.

Table 2 Apalutamide Dose Modification

Severity	Intervention
----------	--------------

Grade 1	
 • Continue apalutamide at current dose • Initiate dermatological treatment^a 
 ○ Topical steroid cream AND ○ Oral Antihistamines • Monitor for change in severity^a
Grade 2 (or symptomatic Grade 1)^b	
 • Hold apalutamide for up to 28 days • Initiate dermatological treatment^a 
 ○ Topical steroid cream AND ○ Oral Antihistamines • Monitor for change in severity^a 
 ○ If rash or related symptoms improve, reinitiate apalutamide when rash is Grades≤1. Consider dose reduction at a 1 dose level reduction^c.
Grade 3^d	
 • Hold apalutamide for up to 28 days • Initiate dermatological treatment^a 
 ○ Topical steroid cream AND ○ Oral Antihistamines AND 
Consider short course of oral steroids
 
 • Reassess after 2 weeks, and if the rash is the same or has worsened, initiate oral steroids (if not already done) and refer the subject to a dermatologist 
 ○ Reinitiate apalutamide at a 1 dose level reduction^e when rash is Grades≤1. ○ If the dose reduction will lead to a dose less than 120mg, the study drug must be stopped (discontinued) • If after 28 days, rash has not resolved to Grades≤1, discontinue study drug
Grade 4	
 • Permanently discontinue apalutamide • Inpatient admission for IV steroids and dermatology consultation

Note: Rash may be graded differently according to the type of rash and associated symptoms. For example, maculo-papular rash is graded by body surface area covered and not severity of the rash. Please consult NCI-CTCAE Version 4.03 for specific grading criteria for other types of rash.

- a** Obtain bacterial/viral cultures if infection is suspected
- b** Subject presents with other rash related symptoms such as pruritus, stinging, or burning
- c** 1 dose level reduction = 60mg (1 apalutamide tablet)
- d** If there is blistering or mucosal involvement, stop apalutamide dosing immediately
- e** If a subject previously started oral corticosteroids, continue for at least 1 week after resumption of reduced dose of apalutamide. If the proposed total oral steroid use will exceed 28 days, contact Principal Investigator.

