10 END OF TREATMENT

A patient may be discontinued from study treatment at any time if the patient or the Investigator feels that it is not in the patient's best interest to continue on study. If a patient's study treatment must be discontinued, this will not result in automatic withdrawal of the patient from the study.

Study treatment with apalutamide will be discontinued for the following reasons, whichever occurs first:

- Disease progression by PCWG criteria. PSA progression is defined as increase of at least 2 ng/mL and 25% above the nadir or baseline on study, whichever is lower, confirmed on repeat measurement at least two weeks later.
- Completion of 13 cycles of study therapy (52 weeks)
- Any episode of seizure
- Any other adverse event that cannot be adequately managed with dose modifications, including dose interruption for treatment-related adverse events that do not improve to Grade 1 or baseline within 14 days, will require study drug discontinuation
- Protocol violation requiring discontinuation of study treatment
- Patient is not compliant with study procedures
- Lost to follow-up
- Patient withdrawal of consent
- Janssen's request for early termination of study

All patients discontinuing study treatment in the absence of disease progression will enter the Post-Treatment Period for PSA monitoring until the time of confirmed PSA progression.

Follow up on study will continue at least the first occurrence of one of the following:

- Disease progression by PCWG criteria.
- Protocol violation requiring discontinuation of study treatment
- Patient is not compliant with study procedures
- Lost to follow-up
- Patient withdrawal of consent
- Janssen's request for early termination of study

If a patient is lost to follow-up, every reasonable effort must be made by the study site personnel to contact the patient and determine the reason for discontinuation/withdrawal. The measures taken to follow up must be documented. When a subject withdraws before completing the study, the reason for withdrawal is to be documented in the CRF and in the source document. Study drug assigned to the withdrawn subject may not be assigned to another subject. Subjects who withdraw will not be replaced.

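### Section 5.3.5 gives two incompatible instructions for a non-rash, treatment-related toxicity that recurs at Grade 4 after a Grade 3 event: go down one dose level, or stop apalutamide permanently

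*Combined protocol and SAP*

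**What the plan says.** **Recurrent toxicity.** The Grade 3 bullet of Section 5.3.5 covers Grade 3 treatment-related events other than seizure. Drug is held and may be resumed one level lower once the event has settled. The bullet then adds: "If toxicity recurs at Grade 3 or higher, the dose of apalutamide should be reduced to the next lower dose level". It allows at most two reductions; Table 1 gives the levels as 240, 180 and 120 mg.

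The next bullet deals with treatment-related events of Grade 4. It exempts insignificant laboratory changes that clear within two days; for all others, "study treatment must be permanently discontinued". It does not separate a first occurrence from a recurrence.

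**Section 10.** The list opens: "Study treatment with apalutamide will be discontinued for the following reasons, whichever occurs first". Its adverse-event entry is "Any other adverse event that cannot be adequately managed with dose modifications", including events that do not improve to Grade 1 or baseline within 14 days. Grade 4 is not named.

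**Seizure.** Section 5.3.5 says "Patients experiencing treatment-related seizure of any grade will have study drug permanently discontinued". Section 10 lists "Any episode of seizure". Section 5.3.5 opens with a condition that links the two: "dose interruptions and/or reductions will be permitted provided that study discontinuation criteria have not been met (please see Section 10".

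**Analysis.** Under Section 12.2.1, a man who stops apalutamide before 12 months for a reason other than progression is inevaluable for the primary endpoint.

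**The concern.** Stopping rules should give one action for one event. Here two adjacent bullets give different actions for the same event, and the event is a severe one: toxicity that has come back at Grade 4 after dosing was resumed. At stake is whether the man is exposed to the drug again.

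Two consequences follow. Section 11 counts dose modifications outside the protocol's specifications as violations, so a site facing this event cannot satisfy both bullets. And the choice feeds into the primary analysis: a man stopped early without progression leaves the evaluable set, while a man continued at a lower dose may stay in it. The trial is open-label (Section 5.2), so whoever chooses the reading knows the arm.

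**Working it through.** This is a comparison of text. The only arithmetic is a context check on power.

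**Step 1. One case under both bullets.** A man has a Grade 3 treatment-related, non-rash toxicity at 240 mg. It settles within two weeks and he resumes at 180 mg. The toxicity recurs at Grade 4 and is not a brief, insignificant laboratory change.

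| Rule in Section 5.3.5 | Does it apply? | Action |
|---|---|---|
| Grade 3 bullet, recurrence sentence | Yes: Grade 4 is higher than Grade 3 | Next lower level, 120 mg by Table 1 |
| Grade 4 bullet | Yes: treatment-related Grade 4, exception not met | Permanent stop |

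Both apply and the actions exclude each other.

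**Step 2. Does another passage settle it?**
- The opening condition of Section 5.3.5 gives precedence to the Section 10 criteria, but those do not name Grade 4.
- The Section 10 adverse-event entry turns on whether dose modification can manage the event. That sends the reader back to Section 5.3.5.
- Table 2 gives one action for Grade 4, but only for rash.

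**Step 3. Where the conflict does not bite.**
- Rash: Table 2 governs.
- Events that keep drug off for more than 14 days, or do not improve to Grade 1 or baseline within 14 days: the last bullet of Section 5.3.5 and Section 10 lead to stopping on either reading.
- A man already at 120 mg: no lower level remains.

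What is left is a non-rash Grade 4 recurrence that settles within 14 days in a man with at least one reduction still available.

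**Step 4. Seizure.** Section 10 stops apalutamide for every seizure. Section 5.3.5 names the treatment-related subset, and its opening sentence defers to Section 10. For a seizure judged unrelated, Section 10 says stop and Section 5.3.5 gives no instruction to continue.

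**Step 5. Context for the analysis.** Inputs from Section 12.2.5: 30 men per arm, 10% inevaluable, 25% versus 2.5%, one-sided 0.10, Fisher's exact test.
- Evaluable per arm: 30 × 0.9 = 27; allowance 30 − 27 = 3.
- Power is the sum, over all outcome pairs (x, y) with one-sided Fisher p ≤ 0.10, of Bin(x; n₁, 0.25) × Bin(y; n₂, 0.025), where n₁ is the SBRT arm.
- n₁ = n₂ = 27: 83.6%, against 84% stated. The plan's figure reproduces.
- One evaluable man fewer: 81.4% if lost from the SBRT arm (26 and 27), 79.2% if lost from the monotherapy arm (27 and 26).

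The last line is conditional on such an event occurring and being handled by stopping. It is not an expected loss.

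**The case against.** **The Grade 4 bullet plainly wins.** It says *must* where the recurrence sentence says *should*, and it is specific to Grade 4. This is a fair reading, and many sites would adopt it. But the recurrence sentence is specific to recurrence, which points the other way, and no sentence ranks the two.

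**The words *or higher* may refer only to the excepted laboratory changes.** Some Grade 4 events do remain outside the mandatory stop. But the recurrence sentence is not limited to them, and the same bullet says that such changes do not require a reduction. The exception narrows the overlap and does not remove it.

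**Seizure.** A reader might infer that the seizure rules also contradict each other, so that an unrelated seizure leads to continued dosing under one section and a stop under the other. The documents do not support that. Section 5.3.5 defers to Section 10, Section 10 covers every seizure, no passage directs continued dosing, and stopping violates nothing. What remains is that a site using the bullet alone might treat attribution as the test.

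**Recurrence after the second reduction.** A reader might also call this unaddressed. It is largely covered by the cap of two reductions together with the Section 10 entry on events that dose modification cannot manage.

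**Size.** One man is a third of the three-man allowance per arm, but that is arithmetic on a planning assumption and not an effect size. Nor does continuing at a lower dose by itself keep a man evaluable: he must still avoid a later early stop, withdrawal and loss to follow-up. Section 1.1.3 reports no seizures and one dose-limiting Grade 3 event among 30 men in Phase I. That suggests such events are uncommon, but the men were spread over doses from 30 to 480 mg, and it gives no rate of Grade 4 recurrence.

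**Conclusion.** Wrong as written, on a narrow point. For a treatment-related, non-rash toxicity that recurs at Grade 4 after a Grade 3 event, outside the brief laboratory exception, Section 5.3.5 orders both a one-level reduction and a permanent stop, and nothing in Section 5.3.5 or Section 10 decides between them.

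The weight of the point is patient safety. The statistical consequence is secondary: different readings across sites can change who is evaluable under Section 12.2.1. Its size cannot be computed from the documents. The stated 84% power is reproduced and is not in question.

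The seizure wording is a mismatch of scope and a minor item. The conclusion rests on reading the two bullets literally and on there being no ranking rule elsewhere in the protocol.

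**What to change.** Reconcile the recurrence sentence in the Grade 3 bullet with the Grade 4 bullet, so that each grade at recurrence leads to exactly one action, and state whether the laboratory exception applies at recurrence. The sponsor chooses the clinical rule; this review takes no view on which is right. Carry the same wording into Section 10, so that the dosing section and the discontinuation list agree.

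As a secondary edit, use one seizure trigger in Sections 5.3.5 and 10, and say whether attribution matters.

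Cost: a few sentences in a protocol amendment. No new procedures, visits or data, and no change to the sample size.

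### The immediate stop for blistering is marked only on the Grade 3 rash row, so a blistering Grade 1 rash with no other listed sign or symptom has a written instruction to continue apalutamide

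*Combined protocol and SAP*

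**What the plan says.** All the rash provisions are in Section 5.3.5 of the protocol.

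- **Rash paragraph, above Table 2.** "If the skin rash has any component of desquamation, mucosal involvement, or pustules, stop dosing with apalutamide". It goes on to require dermatology referral and to recommend a skin biopsy. It has no grade limit and applies "in addition to the interventions listed in below Table".
- **Table 2, Grade 1.** "Continue apalutamide at current dose", with topical steroid, antihistamine and monitoring.
- **Table 2, Grade 2 or symptomatic Grade 1.** Hold for up to 28 days and restart once the rash is Grade 1 or lower. Footnote b defines symptomatic: "Subject presents with other rash related symptoms such as pruritus, stinging, or burning".
- **Table 2, Grade 3.** Hold for up to 28 days. This row alone carries footnote d: "If there is blistering or mucosal involvement, stop apalutamide dosing immediately".
- **Table 2, Grade 4.** Permanent discontinuation.
- **Note under Table 2.** It gives as an example that "maculo-papular rash is graded by body surface area covered and not severity of the rash", and refers the reader to CTCAE 4.03 for other rash types.

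Two general provisions also bear on the point. For treatment-related events of Grades 1-2, Section 5.3.5 says that "short treatment breaks can be instituted as per the discretion of the Investigator". Section 10 opens: "A patient may be discontinued from study treatment at any time if the patient or the Investigator feels" that continuing is not in the patient's best interest.

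**The concern.** Footnote d treats blistering and mucosal involvement alike: either one means an immediate stop. Mucosal involvement is also in the rash paragraph, so its stop applies at every grade. Blistering is not, so its stop applies only where footnote d is marked. The document gives no reason for the difference.

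The difference matters most at Grade 1, the only row that tells the investigator to carry on dosing. If a rash can blister and still be Grade 1, the written instruction there conflicts with the protocol's own judgement about blistering. At stake is the safety of an individual patient on apalutamide.

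**Working it through.** No arithmetic applies, and the plan gives no figure to reproduce. The check is to set the two stop rules side by side and then follow a blistering rash through the table.

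**Step 1. Which signs each rule names**

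| Sign | Rash paragraph (any grade) | Footnote d (Grade 3 row only) |
|---|---|---|
| Desquamation | yes | no |
| Pustules | yes | no |
| Mucosal involvement | yes | yes |
| Blistering | no | yes |

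Blistering is the only sign that footnote d adds, and the only one of the four whose stop depends on grade.

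**Step 2. Written dosing instruction for a blistering rash with none of the paragraph's three signs**

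| Rash | Source | Instruction |
|---|---|---|
| Grade 1, no footnote b symptom | Grade 1 row | continue |
| Grade 1 with a footnote b symptom | Grade 2 row | hold up to 28 days |
| Grade 2 | Grade 2 row | hold up to 28 days |
| Grade 3 | footnote d | stop immediately |
| Grade 4 | Grade 4 row | discontinue permanently |

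The paragraph names blistering at 0 of 4 grades and footnote d at 1 of 4. Only one line of the five instructs the investigator to continue.

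**Step 3. Does another provision close that line?** The general rule for Grades 1-2 and the opening of Section 10 both use permissive wording. They allow a break or discontinuation and require neither. Footnote b gives an open list, so an investigator could read blistering into it, but blistering is not named.

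**Step 4. Can a blistering rash be Grade 1?** The document does not settle this. Appendix 4 only links to CTCAE 4.03. The note under Table 2 shows that, for maculo-papular rash, a low grade does not by itself rule out an alarming feature. It does not say that a blistering rash would be graded on that scale.

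**The case against.** The strongest case against is that the affected rash may be rare or may not exist. It has to blister, be Grade 1, have no footnote b symptom, and show no desquamation, pustules or mucosal involvement. The grade is set by criteria the document does not contain, and the area-based note covers only one rash type. Investigators can also interrupt or stop treatment whenever they judge it right, and many would do so on seeing blisters.

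Much of this stands. It limits the point to a mismatch in wording, with an unknown clinical frequency. It does not remove the mismatch: the protocol does not leave the other three signs to discretion, and gives no reason to do so for blistering. Explicit wording also has practical value here, because Section 7.1.3 lets examinations after screening be abbreviated, done by other qualified staff, or done by telemedicine.

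A reader might infer three stronger points that the document does not support:

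- **That every blistering Grade 1 rash is continued.** The table itself sends a symptomatic Grade 1 rash to the hold row, with no discretion involved.
- **That low-grade rashes with other alarming signs are also missed.** The rash paragraph applies in addition to the table, so its three signs already stop dosing at Grades 1 and 2.
- **That dermatology referral and biopsy are wrongly missing for blistering.** Footnote d ties blistering to a stop only. Nothing in the protocol links blistering to the paragraph's referral or biopsy advice, so their absence is not an inconsistency.

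**Conclusion.** The point holds in a narrow form. The protocol calls for an immediate stop for blistering but attaches that instruction only to Grade 3. One written path, Grade 1 with no footnote b symptom and none of the three listed signs, therefore tells the investigator to continue. At Grade 2 and for symptomatic Grade 1, dosing is already interrupted. Neither the paragraph nor footnote d calls its stop permanent, so the practical difference from a hold is small.

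The wording mismatch is certain on the text. The clinical consequence rests on the assumption that CTCAE 4.03 allows a blistering rash to be Grade 1, which cannot be checked here. The document gives no rash or blistering rate, so the number of patients affected could be zero. Sample size, power and significance level are unaffected. This is a minor patient-safety consistency correction.

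**What to change.** At the next amendment, mark footnote d on the Grade 1 and Grade 2 rows of Table 2 as well as Grade 3, and add a sentence to the footnote saying that it takes precedence over the Grade 1 instruction to continue. The Grade 1 mark closes the gap. The Grade 2 mark makes the rule uniform and covers symptomatic Grade 1, which is handled in that row.

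The cost is two footnote marks and one sentence, with no added procedure or visit. The small downside is an occasional earlier dose interruption for a patient with a mild blistering rash.

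Adding blistering to the list in the rash paragraph is optional. It would also make the stop apply at every grade, but it would bring a dermatology referral and a recommended skin biopsy that the protocol does not now tie to blistering. That is a clinical choice for the sponsor.

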12.2 ANALYTIC PLAN

12.2.1 Analysis of Primary Endpoint

The primary endpoint for the study is the proportion of patients with undetectable serum PSA (< 0.2 ng/mL) at 6 months following completion of apalutamide therapy (18 months from date of randomization). Fisher's exact test will be used to compare the proportion in the two treatment arms. Patients who discontinue apalutamide prior to completion of 12 months of therapy for reasons other than disease progression by PCWG criteria, as well as patients who withdraw or are lost to follow up, will be considered inevaluable for this analysis. Patients who discontinue treatment for radiographic or clinical progression, even if occurring prior to receipt of SBRT in the experimental arm), would be evaluable for analysis of the primary endpoint.

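### Rash holds of 15 to 28 days: the rash table in 5.3.5 lets apalutamide be held and restarted, while the 14-day rules in 5.3.5 and Section 10 call for discontinuation and make no exception for rash

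*Combined protocol and SAP*

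**What the plan says.** The rash part of section 5.3.5 has its own table (Table 2, Apalutamide Dose Modification; section 9.1.6 has a different table with the same number). For Grade 2 or symptomatic Grade 1 rash, and again for Grade 3 rash, it says "Hold apalutamide for up to 28 days". Restart is allowed once the rash is Grade 1 or lower. The Grade 3 row adds a step at two weeks: "Reassess after 2 weeks, and if the rash is the same or has worsened, initiate oral steroids", together with referral to a dermatologist. It orders a stop for non-resolution only later: "If after 28 days, rash has not resolved to Grades≤1, discontinue study drug".

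The general text uses a 14-day limit in three places:

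- Section 5.3.5, Grade 3 bullet: "If the severity of the toxicity decreases to Grade 1 or returns to baseline within two weeks, study treatment may be resumed".
- Section 5.3.5, delay bullet: "Any patient requiring > 14 days delay in treatment due to study treatment-related AEs should discontinue treatment".
- Section 10, reasons for stopping apalutamide: "dose interruption for treatment-related adverse events that do not improve to Grade 1 or baseline within 14 days, will require study drug discontinuation".

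Section 5.3.5 opens with a condition that points to Section 10: "Intra-patient dose interruptions and/or reductions will be permitted provided that study discontinuation criteria have not been met".

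Section 12.2.1 makes the stopping decision matter for the primary analysis. It classes as inevaluable "Patients who discontinue apalutamide prior to completion of 12 months of therapy for reasons other than disease progression by PCWG criteria", along with patients who withdraw or are lost to follow-up.

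**The concern.** The rash table and the general rules give different instructions for the same patient at the same time. The clearest case is a treatment-related Grade 3 rash that has not improved after two weeks. The table expects this patient, intensifies treatment and keeps the hold open. Section 10 requires that he stop the drug.

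Three things are at stake:

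- **Patient management.** The passages govern permanent discontinuation of the study drug, and a site cannot tell from the text which instruction applies.
- **Protocol compliance.** Section 11 counts dose modifications outside the protocol's specifications as violations. A site that restarts on day 20 follows the rash table and can still be cited under the general rules.
- **The primary analysis set.** Stopping early for toxicity removes a patient from the primary comparison under 12.2.1. In an open-label multicenter trial, the reading a site adopts can therefore influence who is counted.

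**Working it through.** This is a comparison of texts. The only arithmetic is the overlap of the limits and a sense of scale.

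**Conflict window.** The rash table allows up to 28 days and the general limit is 14 days. 28 − 14 = 14, so the conflict covers days 15 to 28, which is 14 of the 28 hold days permitted. The 28 days is a ceiling, so a site that stops by day 14 breaches nothing in the table. The conflict arises only when a hold runs past day 14.

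**One patient through the text: treatment-related Grade 3 rash, unchanged at day 14, Grade 1 on day 20.**

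- Up to day 14, all passages agree that the drug is held.
- At day 14, the rash table calls for oral steroids and referral, and the hold continues. The Section 10 trigger is met, because the rash has not reached Grade 1 or baseline in 14 days.
- From day 15, the delay bullet in 5.3.5 is also met.
- On day 20, the rash table restarts apalutamide one dose level lower. Under Section 10 the drug has already been stopped for good.

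**By grade, for a hold beyond 14 days.**

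- Grade 3: conflicts directly with the delay bullet and, if the rash is not at Grade 1 or baseline by day 14, with Section 10. It also conflicts by implication with the Grade 3 bullet, which ties resumption to recovery within two weeks but does not itself order a stop.
- Grade 2: conflicts with the delay bullet, and with Section 10 if the rash is still Grade 2 at day 14.
- Symptomatic Grade 1: clearly conflicts only with the delay bullet, because the Section 10 trigger is failure to reach Grade 1 or baseline.

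**Is there an exception or an order of precedence?** The sentence introducing the rash table says the modifications are summarized there. It does not say the table replaces other rules. The delay bullet applies to any patient. The general bullets state exceptions where they are meant: seizure is carved out of the Grade 3 bullet, and clinically insignificant laboratory abnormalities are addressed in the Grade 3 and Grade 4 bullets. Rash appears in none of them. The one sentence that bears on precedence, the opening of 5.3.5, makes interruptions subject to Section 10.

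**Scale.** The inputs from 12.2.5 are 30 patients per arm, 10% inevaluable or dropped out, 25% versus 2.5%, and Fisher's exact test at one-sided 0.10.

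- Planned allowance: 10% × 30 = 3 per arm, leaving 27 evaluable.
- Power is the sum of Bin(x; 27, 0.25) × Bin(y; 27, 0.025) over all pairs (x, y) with one-sided Fisher p ≤ 0.10. The result is 83.6%, which reproduces the stated 84%.
- One patient is 1/30 = 3.3% of an arm. If each arm lost one more evaluable patient (26 per arm), the same calculation gives 81.9%, a fall of 1.7 points.

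The documents give no frequency of rash holds longer than 14 days, so these figures show what one patient is worth. They do not estimate the effect.

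**The case against.** The best counter-argument is that the rash table is the specific rule and displaces the general one. It sits under its own heading directly after the general bullets, it addresses the two-week point explicitly and chooses escalation, and it sets its own stop at 28 days. It looks deliberate, and may well be. But the displacement has to be inferred, and the opening line of 5.3.5 points the other way.

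A second argument concerns the start of the Section 10 bullet, which speaks of events that dose modification cannot adequately manage. A rash improving under the rash table might be said to fall outside it. However, the bullet goes on to include, by name, interruptions for events not improved to Grade 1 or baseline within 14 days, which is the case at issue.

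Third, the general bullet for Grade 1 and 2 events allows short breaks at the investigator's discretion with no number of days. That softens the Grade 2 and symptomatic Grade 1 cases, but it does not suspend the delay bullet.

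Some of the objection stands. The 14-day statements differ in force: Section 10 is mandatory, the delay bullet says patients should stop, and the Grade 3 bullet conflicts only by implication. Both arms take apalutamide under the same rules, so the documents give no reason to expect the ambiguity to favour one arm. The consequence for the analysis is possible but unquantified.

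**Conclusion.** The contradiction is real. For treatment-related rash held 15 to 28 days, the rash table permits continuing the hold and restarting, while the delay bullet in 5.3.5 calls for discontinuation. Section 10 requires discontinuation if the rash has not reached Grade 1 or baseline by day 14. No text resolves this.

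It should be corrected because it concerns permanent discontinuation and can affect membership of the primary analysis set. It does not decide membership alone: a patient who restarts stays evaluable only if he then completes 12 months or stops for progression, and is not withdrawn or lost. The conclusion applies only to rash judged treatment-related. The size of the effect is unknown, and the sample-size calculation is not challenged. No view is taken on which limit is right.

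**What to change.** Reconcile three places so that a single hold limit governs rash: the rash table in 5.3.5, the delay and Grade 3 bullets in 5.3.5, and the 14-day bullet in Section 10.

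- If rash is meant to be an exception, say so in the general bullets of 5.3.5 and in Section 10.
- If it is not, align the rash table, including its two-week and 28-day steps, with the 14-day rules.

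The clinical team decides which applies. The cost is a wording change in these passages, made as an amendment under section 13.5. It adds no visits, procedures or data collection.
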